12.0 CRITERIA FOR TREATMENT DISCONTINUATION

Participants may discontinue study intervention at any time for any reason or be dropped from the study intervention at the discretion of the investigator should any untoward effect occur. In addition, a participant may be discontinued from study intervention by the investigator if study intervention is inappropriate, the study plan is violated, or for administrative and/or other safety reasons. Specific details regarding procedures to be performed at study intervention discontinuation are provided in Sections 11.4 and 11.5.

A patient will be discontinued from study treatment under the following circumstances:

- Progressive disease (PD) as per RECIST v1.1 or the subject no longer experiences clinical benefit as determined by the investigator (see Section 12.1 for criteria for continuing treatment beyond progression).
- Unacceptable toxicities despite supportive therapy and dose reduction/modification.

- Discontinuation of pembrolizumab for recurrent grade 2 pneumonitis.
- An AE or intercurrent illness/condition or personal circumstance which, in the opinion of the investigator, places the participant at unnecessary risk from continued administration of study intervention.
- Any progression or recurrence of another malignancy, or any occurrence of another malignancy that requires active treatment.
- Constraints of this protocol are detrimental to the patient's health.
- Necessity for treatment with other anticancer agents or other treatment prohibited by protocol.
- TRAE that results in interruption of cabozantinib > 4 weeks and pembrolizumab > 12 weeks, unless there is unequivocal evidence that the subject is benefitting. In this situation, a subject may be able to restart therapy upon resolution of the toxicity and with agreement of the Study PI.
- Patient requests discontinuation.
- Sexually active subjects who refuse to use medically accepted barrier methods of contraception (Appendix 8) during the course of the study and for 4 months after discontinuation of study treatment.
- Women who become pregnant or are breastfeeding.
- Request by regulatory agencies for termination of treatment of an individual subject or all subjects under the protocol.
- Significant noncompliance with the protocol schedule in the opinion of the investigator.
- Discontinuation of pembrolizumab may be considered for participants who have attained a confirmed CR and have been treated for at least 8 cycles (at least 24 weeks), receiving at least 2 further cycles of cabozantinib and pembrolizumab beyond the date when the initial CR was declared.
- Completion of 2 years of therapy.
- Participant has any of the following non-overdose HECIs that are not reversible and manageable by therapy (see below). (Note: Temporary hepatic decompensation may occur in patients with cirrhosis exposed to TKIs.)
 - ALT >20 × ULN (confirmed within 1 week)
 - Drug-related total bilirubin >10 × ULN
 - CP score of > 8 points
 - Hepatic encephalopathy
 - Recurrence of a severe or life-threatening event, or of any of the laboratory abnormalities listed above, that are presumed to be immune-related
 - Uncontrolled ascites
- Subject is lost to follow-up.

Patients who come off study should be evaluated at 30 days (+ 7 days) after the last dose of cabozantinib or pembrolizumab (whichever is latest). AE assessment and reporting for patients who discontinue study treatment are described in Section 16.3.2. Furthermore, subjects who come off study for reasons other than PD will be followed for progression, and all patients who come off study will be followed for survival every 4 months for up to 2 years from study start date.

12.1 Treatment beyond progression

Cases of pseudo-progression have been documented in certain tumor types treated with immune-oncology agents.⁶⁰ Patients with initial disease progression on imaging (i.e. PD by RECIST v1.1, iUPD by iRECIST, see Section 13.0) may be allowed to continue on study treatment if they meet all of the criteria below:

- Patient is tolerating treatment.
 - Note: Patients are allowed to continue beyond progression on monotherapy cabozantinib (any dose) or pembrolizumab if the other agent was previously discontinued due to toxicity.
- Patient is deriving clinical benefit from ongoing treatment as assessed by the investigator.
- Patient continues to meet eligibility criteria.
- Disease progression is asymptomatic and does not pose a risk of a serious complication (e.g. progression in vertebral metastasis expected to lead to fracture or cord compression with further growth).
- Patient has stable ECOG performance status and is not expected to decline in the near future.
- Treatment beyond progression will not delay an imminent intervention to prevent serious complications of disease progression (e.g. radiation to CNS metastases).

Patients who meet the above criteria and continue study treatment beyond progression must sign a consent form to do so.

If a patient continues treatment beyond progression, repeat imaging will be obtained at 4 weeks to confirm PD (i.e. iCPD by iRECIST). If there is confirmed disease progression, it is generally recommended that the study treatment be discontinued. However, if the patient appears to be deriving clinical benefit from treatment and is clinically stable, treatment beyond confirmed PD may be continued with permission obtained from the PI. If disease appears stable and PD cannot be confirmed on subsequent scans (i.e. response remains iUPD), then the patient may continue on study as long as clinically stable. See Section 13.2 for iRECIST criteria. Table 12.1.1 provides guidance on treatment after radiologic evidence of PD.

Table 12.1.1. Imaging and treatment after first radiologic evidence of progressive disease.

	Clinically Stable		Clinically Unstable	
	Imaging	Treatment	Imaging	Treatment
First radiologic evidence of PD by RECIST 1.1	Repeat imaging at 4 to 8 weeks to confirm PD.	May continue study treatment at the Investigator's discretion while awaiting confirmatory tumor imaging by site by iRECIST.	Repeat imaging at 4 to 8 weeks to confirm PD per Investigator's discretion only.	Discontinue treatment
Repeat tumor imaging confirms PD (iCPD) by iRECIST per Investigator assessment	No additional imaging required.	Discontinue treatment (exception is possible upon consultation with	No additional imaging required.	Not applicable

Principal Investigator				
Repeat tumor imaging shows iUPD by iRECIST per Investigator assessment	Repeat imaging at 4 to 8 weeks to confirm PD. May occur at next regularly scheduled imaging visit.	Continue study treatment at the Investigator's discretion.	Repeat imaging at 4 to 8 weeks to confirm PD per Investigator's discretion only.	Discontinue treatment
Repeat tumor imaging shows iSD, iPR, or iCR by iRECIST per Investigator assessment.	Continue regularly scheduled imaging assessments.	Continue study treatment at the Investigator's discretion.	Continue regularly scheduled imaging assessments.	May restart study treatment if condition has improved and/or clinically stable per Investigator's discretion. Next tumor image should occur according to the regular imaging schedule.

iCPD = iRECIST confirmed progressive disease; iCR = iRECIST complete response; iRECIST = modified Response Evaluation Criteria in Solid Tumors 1.1 for immune-based therapeutics; iSD = iRECIST stable disease; iUPD = iRECIST unconfirmed progressive disease; PD = progressive disease; RECIST 1.1 = Response Evaluation Criteria in Solid Tumors 1.1.

13.0 GUIDELINES FOR DISEASE EVALUATION

The primary endpoint of this study is ORR by RECIST v.1.1. Secondary endpoints include DCR by RECIST v1.1, as well as ORR and DCR by iRECIST. Response criteria will be assessed by a central radiology team (OncoRad) at the University of Washington.^{60,61}

13.1 Tumor assessment by RECIST v1.1 (primary endpoint)

13.1.1 Definitions for measurable disease and target lesions

Criteria for target lesions

- Lesions that are ≥ 10 mm (long axis) on CT (slice thickness 5 mm or less) orMRI
- Lymph nodes must be ≥ 15 mm (short axis) on CT (slice thickness 5 mm or less) orMRI
- Up to 5 target lesions in total can be reported, and a maximum of 2 lesions perorgan
- Target lesions should be the largest and most reproducible lesions on repeatassessments
- Target lesions should be representative of all involvedorgans

Notes:

- The lymphatic system is considered one organ in RECIST v1.1. Therefore, a maximum of 2 lymph nodes that are classified as target lesions should be reported on the RECIST CRF.
- Lesions that were previously radiated or ablated cannot be target lesions unless there was subsequent radiographic progression at those sites.

Criteria for non-target lesions

- Any lesions that don't meet the criteria for target lesions or are above the reporting limit for target lesions
- All other sites of disease that are <10 mm (long axis) on CT or MRI
- Lymph nodes that are ≥ 10 to <15 mm in the short axis on CT or MRI
- Lesions truly non-measurable such as ascites, leptomeningeal disease, pleural and pericardial effusion, inflammatory breast disease, lymphangitic involvement of skin or lung
- Lesions that are not suitable for repeat measurement, e.g. abutting other structures or likely to coalesce with other lesions
- Multiple non-target lesions in the same organ should be reported as a single non-target lesion, e.g. multiple liver metastases

Note: The lymphatic system is considered one organ in RECIST v1.1. Therefore, multiple lymph nodes that are classified as non-target lesions should be reported as a single non-target lesion on the RECIST CRF.

Measurable disease

- Lesions that can be accurately measured in the longest dimension as ≥ 10 mm by CT scan, ≥ 20 mm by chest X Ray, ≥ 10 mm by caliper on clinical exam. Malignant lymph nodes need to be ≥ 15 mm (short axis) on CT.

Non-measurable disease

- All other lesions that do not fit the criteria for measurable disease. All definitions are outlined in RECIST v1.1 reference.⁶¹

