5.1 Inclusion criteria

1. At least 18 years of age.
2. Must have a histologically confirmed diagnosis of HCC or a non-invasive diagnosis of HCC as per the American Association for the Study of Liver Diseases (AASLD) criteria.
 - c. If available, archival tissue must be submitted.
 - d. Mixed HCC-cholangiocarcinoma is not allowed.
3. Patient has BCLC stage C disease, or BCLC stage B disease that is not amenable to locoregional therapy or refractory to locoregional therapy, and not amenable to curative treatment.
 - a. Previous locoregional therapy is allowed (e.g. surgical resection, external beam radiation, catheter-based therapy), and patients must have evidence of disease progression from locoregional therapy.
4. Must have measurable disease by RECIST v1.1.
 - a. Lesions that were previously radiated or ablated cannot be target lesions unless there was subsequent radiographic progression at those sites.

RG1007034

5. No prior systemic therapy for HCC. Prior chemotherapy given locally into the liver (e.g. TACE) is allowed.
6. Must have Child-Pugh class A hepatic function within 7 days prior to first dose of study intervention (Appendix 6).
7. ECOG performance status 0-1 (Appendix 5).
8. Life expectancy of at least 12 weeks.
9. Recovery to baseline or \leq Grade 1 toxicities (CTCAE v5) related to any prior treatments, unless adverse events (AEs) are clinically nonsignificant and/or stable on supportive therapy.
10. Adequate organ and marrow function, based upon meeting all of the following laboratory criteria within 14 days before first dose of study treatment:
 - a. Absolute neutrophil count (ANC) $\geq 1500/\text{mm}^3$ without granulocyte colony-stimulating factor support.
 - b. Platelets $\geq 60,000/\text{mm}^3$ without transfusion within 14 days.
 - c. Hemoglobin $\geq 9 \text{ g/dL}$ ($\geq 90 \text{ g/L}$) without transfusion or EPO dependency within 14 days.
 - d. Alanine aminotransferase (ALT) and aspartate aminotransferase (AST) $\leq 5 \times$ upper limit of normal (ULN).
 - e. Total bilirubin $\leq 2 \text{ mg/dL}$ OR direct bilirubin $\leq \text{ULN}$ for participants with total bilirubin levels $>2 \text{ mg/dL}$.
 - f. Serum albumin $\geq 2.8 \text{ g/dL}$ ($\geq 28 \text{ g/L}$) without albumin infusion.
 - g. Prothrombin time (PT)/INR or partial thromboplastin time (PTT) test $\leq 1.5 \times \text{ULN}$.

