8.4 Prohibited or restricted therapy

The following therapies are prohibited from the time of screening until study treatment has been permanently discontinued:

- Any investigational agent or investigational medical device.
- Oral anticoagulants (e.g. warfarin or other coumarin-related agents, direct thrombin or direct FXa inhibitors, antiplatelet agents such as clopidogrel, or chronic use of aspirin above low dose levels for cardioprotection per local applicable guidelines).
- Any non-protocol systemic anticancer treatment (e.g. chemotherapy, immunotherapy, radionuclides, drugs or herbal products used specifically for the treatment of the cancer under investigation).
- Local anticancer treatment including palliative radiation, ablation, embolization, or surgery on target lesions used for response monitoring by RECIST v1.1.
 - Note: radiation therapy to a symptomatic solitary lesion or to the brain that is not a target lesion may be allowed at the investigator's discretion.
- Anti-HCV therapy.
- Live vaccines or live attenuated within 30 days prior to the first dose of study treatment and while participating in the study. Administration of killed vaccines is allowed.
- Systemic glucocorticoids for any purpose other than to modulate symptoms from an event of clinical interest of suspected immunologic etiology. The use of physiologic doses of corticosteroids may be approved after consultation with the Principal Investigator.

Subjects who, in the assessment by the investigator, require the use of any of the aforementioned treatments for clinical management should be removed from the study.

The following therapies should be avoided until study treatment has been permanently discontinued or until otherwise specified:

- Erythropoietic stimulating agents (e.g. epoetin alfa and darbepoetin alfa) should not be used based on a report of increased risk of tumor recurrence/progression associated with erythropoietin (Wright et al 2007).
- Concomitant medications that are known to prolong the QTc interval should be avoided in subjects who receive cabozantinib until they have permanently discontinued cabozantinib treatment (refer to <http://www.qtdrugs.org> for a list of drugs which have the potential to prolong the QTc interval).
- Chronic co-administration of cabozantinib with strong inducers of the CYP3A4 family (Appendix 4)

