11.0 STUDY ASSESSMENTS

11.1 Baseline/screening evaluations

Within 28 days prior to registration:

- Informed consent and HIPAA authorization will be obtained according to ICH/GCP guidelines prior to performing any study-specific procedures.
- Medical and smoking history will be recorded.
 - Medical history must include all active conditions and any condition diagnosed within the prior 10 years that are considered to be clinically significant by the investigator. Details regarding the disease for which the participant has enrolled in this study will be recorded separately and not listed as medical history.
- Disease details and treatments will be recorded.
 - This information will include: BCLC stage at diagnosis and current BCLC stage, and all prior cancer treatments (e.g. surgery, ablation, liver-directed therapy).
- Assessment of vital signs, physical examination, assessment of ECOG status, weight, height, baseline AEs and medications.
 - Medication history will include any prior medication use within 28 days before starting on study, including indication and any protocol-related washout requirement. Treatment for the disease for which the participant has enrolled in this study will be recorded separately and not listed as a prior medication.
- Assessment of eligibility based on inclusion/exclusion criteria by treatment investigator (Section 5.0).
- Multiphasic contrast CT or MRI of abdomen/pelvis and CT chest with or without contrast for baseline disease assessment, as well as confirmation of measurable disease and at least 1 appropriate target lesion per RECIST v1.1. As clinically indicated, bone scan and contrast-imaging of neck may be obtained.
- Archival tissue will be requested if available. If archival tissue is not available, an optional fresh core biopsy may be performed (if safe and feasible).
 - For patients who had prior next-generation gene sequencing analysis of their tumor, the gene sequencing assay results will be requested.

Within 14 days prior to registration:

- CBC with differential (including hemoglobin, hematocrit, leukocyte count, neutrophils, lymphocytes, monocytes, eosinophils, basophils, and platelets).
- Serum chemistry (including sodium, bicarbonate, potassium, calcium, magnesium, phosphate, glucose, albumin, total protein, blood urea nitrogen, creatinine, alanine aminotransferase, aspartate aminotransferase, alkaline phosphatase, and total bilirubin).

- PT/INR and PTT.
- Lactate dehydrogenase (LDH)

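### The target-lesion rule names radiated and ablated lesions but not embolised ones, so a TACE-treated lesion that has not itself progressed can count towards the primary ORR

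*Combined protocol and SAP*

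**What the plan says.** The rule appears with the same wording in inclusion 4a of the synopsis, inclusion 4a of Section 5.1 and the notes to Section 13.1.1: "Lesions that were previously radiated or ablated cannot be target lesions unless there was subsequent radiographic progression at those sites".

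Prior liver-directed treatment is admitted in two places in Section 5.1. Item 3a says "Previous locoregional therapy is allowed (e.g. surgical resection, external beam radiation, catheter-based therapy", and adds that "patients must have evidence of disease progression from locoregional therapy". Item 5 says "Prior chemotherapy given locally into the liver (e.g. TACE) is allowed".

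Section 8.4 opens its list of barred treatments with "The following therapies are prohibited from the time of screening until study treatment has been permanently discontinued". One entry is "Local anticancer treatment including palliative radiation, ablation, embolization, or surgery on target lesions used for response monitoring by RECIST v1.1".

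On choosing targets, Section 13.1.1 says "Target lesions should be the largest and most reproducible lesions", with at most five in total and two per organ. Section 11.1 asks at baseline for "confirmation of measurable disease and at least 1 appropriate target lesion per RECIST v1.1". Response is read by blinded central review (Section 4.1). Section 13.1.2 defines PR as a fall of at least 30% from baseline in the target sum.

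**The concern.** The plan already accepts that a locally treated lesion is a poor target unless it has since grown at that site, because its later size may reflect the earlier procedure and not the study drugs. It applies this to radiation and ablation but leaves out embolisation, a local treatment that its own eligibility criteria permit.

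A patient could therefore have a TACE-treated liver lesion that is not growing, progress elsewhere, enter the trial, and have the treated lesion measured as a target. Two errors are then possible. Late shrinkage from the embolisation could contribute to a PR that the study drugs did not produce. Alternatively, a treated lesion that no longer changes in size could dilute the sum and hide a real PR in the untreated disease. The trial has no control arm, so neither error is offset by a comparison group.

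**Working it through.** **1. The plan's own figures.** Inputs from Section 17.1: 13 patients in stage 1, stop at 2 or fewer responses; 29 in total, reject at 9 or more; ORR 20% (null) and 38% (alternative). The exact rejection probability is

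P(reject | p) = Σ over x = 3 to 13 of Bin(x; 13, p) × P[Bin(16, p) ≥ max(0, 9 − x)].

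This gives 0.0999 at p = 0.20 and 0.8044 at p = 0.38, matching the stated 0.10 and 80%. The design arithmetic is not in dispute.

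**2. Does the wording cover embolised lesions?**

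- Inclusion 4a and 13.1.1 name radiation and ablation only.
- Section 8.4 lists ablation and embolization as separate items, so ablation does not plainly include embolisation.
- Radioembolisation can be read as radiation. The gap is clearest for TACE and bland embolisation.

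**3. Does another provision close the gap?**

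- Inclusion 3a requires progression from locoregional therapy but, unlike 4a, does not say where. Progression elsewhere can satisfy it.
- Exclusion 5 is a 4-week washout for liver-directed therapy. It governs timing, not lesion choice.
- Section 8.4 protects target lesions from screening onward and does not reach earlier procedures.
- The preference for large, reproducible lesions (13.1.1) and the word appropriate (11.1) let a reader pass over such a lesion but do not require it. Size may even favour it.
- Section 11.3 records previous treatments, their dates and best response, but mentions no link to individual lesions.

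**4. How one lesion can decide a PR (constructed example).** Take a 60 mm embolised target and a 30 mm untreated target. The baseline sum is 90 mm, and PR needs a fall of 0.30 × 90 = 27 mm.

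- Untreated lesion unchanged: the embolised one must shrink 27/60 = 45%.
- Untreated lesion grows 20% (6 mm): the embolised one must shrink (27 + 6)/60 = 55%.
- Embolised lesion static: the untreated one must shrink 27/30 = 90%.

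In general, if a static lesion makes up a share w of the baseline sum, the other targets must shrink by 0.30/(1 − w): 43% at w = 0.3, 60% at w = 0.5 and 100% at w = 0.7. Under the table in 13.1.3, a new lesion or progression of a non-target lesion makes the overall response PD whatever the target sum does, which limits false PRs.

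**5. What one patient is worth.** One responder is 1/29 = 3.4 percentage points. The final decision changes between 8/29 (27.6%, not rejected) and 9/29 (31.0%, rejected). The chance of passing stage 1 and finishing on exactly 8 is 0.083 at a true ORR of 20%. The chance of finishing on exactly 9 is 0.104 at 38%. These are properties of the design. They do not say how often a patient would be misclassified.

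**The case against.** The strongest reply is that the endpoint is response by RECIST v1.1, read by a central radiology team with the RECIST paper cited, and that 11.1 asks for an appropriate target under that standard. If the paper contains a broader rule on treated lesions, practice may already be sound. That source is not among the documents. The general pointer to it in 13.1.1 sits under non-measurable disease, and the protocol states its own, narrower rule. If readers are meant to apply something wider, the protocol should say so.

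Second, inclusion 3a can be read as progression of the treated disease, and BCLC B entry is limited to disease not amenable or refractory to locoregional therapy. Both make an embolised, non-progressed target less likely, and the washout in exclusion 5 removes the most recent procedures. This stands as a limit on frequency. It does not exclude the case.

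Third, the protocol's lists of local treatments are loose and differ between Sections 5.1, 8.4, 11.1 and 11.3, so one list separating ablation from embolization is weak evidence of intent. That is fair. The point is that the text leaves the matter open, not that the authors meant to admit such lesions.

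A reader might go further and infer that type I error is inflated or power lost by a definite amount. The documents do not support that. They give neither the share of patients with such a target nor the rate at which it would change a response, and the two errors push ORR in opposite directions. Any such figure would come wholly from assumed inputs.

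**Conclusion.** The gap in the wording is real. Under the rule as written, a lesion treated by TACE or bland embolisation that has not itself progressed is an allowable target for the primary ORR, and no other provision in the documents prevents it. This reading assumes that embolisation is not a form of ablation, as the list in 8.4 suggests, and that the central readers follow the protocol's text and not a wider rule from the cited paper.

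The effect is unquantified and its net direction unknown. It would not be correct to infer that the planned ORR is biased upward, or that the stated 0.10 and 80% are wrong. What can be said is that the final decision can turn on one patient and that one lesion can settle a patient's response class. The 20% benchmark does not resolve the direction either, since the documents do not say how embolised lesions were handled when it was measured.

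Severity is minor. This is a cheap improvement to the definition of the primary endpoint.

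**What to change.** In inclusion 4a (synopsis and Section 5.1) and in Section 13.1.1, extend the treatments named at the start of the rule to: radiated, ablated or embolised (e.g. TACE or other catheter-based therapy). Leave the exception for later progression at the treated site unchanged. This also settles how radioembolisation is handled.

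Add one field to the treatment history in Section 11.3 that identifies which lesions were treated. Make it available when targets are chosen at baseline, with the central readers otherwise blinded as planned.

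The cost is a few words in three places and one lesion-level data field. An occasional patient will need a different target lesion, or will be ineligible if the only measurable lesion is embolised and has not progressed. The protocol already accepts that consequence for radiated and ablated lesions. The sample size and decision rule do not change.
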